²If the subject has an active, ongoing medical condition, the condition cannot meet any of the following criteria: 1.) first diagnosed within 3 months of enrollment; 2.) is worsening in terms of clinical outcome in last 6 months; or 3.) involves need for medication that may pose a risk to subject's safety or significantly impede assessment of adverse events if they participate in the study.

8) Subjects with a body mass index (BMI) (weight in kg divided by height in m, squared) between 18.5 and/or 35.0 kg/m², inclusive, and a minimum weight of 50 kg;

9) Subjects must refrain from strenuous physical activity that could cause muscle aches or injury, including contact sports, at any time from screening until completion of the trial.

10) Subjects must refrain from over-the-counter and-prescription medications¹ and nutritional supplements within 14 days before first study drug administration, and until after the final study visit.

¹except for hormonal contraceptives, acetaminophen or ibuprofen.

11) Subject has adequate venous access for blood collection.

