5.1.2 Subject Exclusion Criteria

Subjects must NOT meet any of the following exclusion criteria:

- 1) History of any hypersensitivity or allergic reaction to echinocandins or excipients (mannitol, polysorbate 80, histidine) of the rezafungin for injection and rezafungin for infusion formulations.
- 2) Subjects presenting with a clinically significant condition;⁵

⁵Subjects with any of the following must not be included into the study: clinically significant oncologic, infectious, cardiovascular, pulmonary, hepatic, gastrointestinal, hematologic, metabolic, endocrine, neurologic, immunologic, renal, psychiatric, or other condition that in the opinion of the Investigator would preclude the safe participation of the subject in the study or would prevent the subject from meeting the study requirements.

- 3) Any condition that in the opinion of the Investigator could significantly impact drug absorption, distribution, or elimination;
- 4) Symptoms of acute illness or chronic disease within 14 days of initial dosing;
- 5) Positive screen for hepatitis B virus surface antigen, hepatitis C virus antibody, or HIV antibody;
- 6) Subjects with clinical laboratory values outside the site reference ranges¹ prior to initial dosing;

¹Clinical laboratory values outside the site reference ranges, if considered by the site investigator to be clinically insignificant, are acceptable if not exceeding Grade 1 severity. One repeat of lab testing is allowed to make this determination during screening.

- 7) Abnormal ECGs. See [Section 7.1 Clinical Evaluations](#) for exceptions;
- 8) Female subject of childbearing potential who is pregnant,⁶ lactating, or planning to become pregnant during the study period or at least 30 days after the final dose of study product;

⁶Having a positive serum pregnancy test at the Screening Visit or any other specified time point prior to the dose of study product.

- 9) Received any prescription medications (except for hormonal contraceptives) within 14 days before first study drug administration;

10) Received any non-prescription medications, vitamins, herbal or dietary supplements⁷ within 14 days of initial dosing, unless prior approval is granted by both the Investigator and the Sponsor;

⁷Excluded from this list is intermittent use of acetaminophen at doses of ≤ 2 g/day or ibuprofen ≤ 1200 mg/day. However, acetaminophen only is accepted to treat AEs for pain (i.e. headaches) during in-clinic stay.

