11) Current smoker or tobacco⁸ use within 90 days prior to screening or while a subject is enrolled in the study;

⁸Tobacco use includes vaping, smoking tobacco, the use of snuff and chewing tobacco, and other nicotine or nicotine- containing products

12) History of illicit/illegal drug use prior to dosing or while a subject is enrolled in the study⁹ or reports an alcohol or substance abuse problem* within 6 months of dosing;

⁹A urine drug test will be performed at screening and upon admission to the CRU. Drug screen includes amphetamines, barbiturates, cocaine, opiates, cannabinoids, phencyclidine, and benzodiazepines.

*Inclusive of vaping of non-nicotine products

13) Consumed foods or beverages containing alcohol or xanthines/caffeine ^{a,b}:

- a. Alcohol: ≤ 48 hours before the first study drug administration, until discharge;
- b. Xanthines/caffeine: ≤ 24 hours before the first study drug administration, until discharge;

14) Received any live or killed vaccines or immunoglobulins within 14 days of dosing;

15) Donated blood or blood products or experienced significant blood loss within 60 days of dosing;

16) Received a blood transfusion within 14 days of dosing;

17) Previous participation in this trial, any other rezafungin trial, or any trial¹⁰ within 28 days of dosing. Plans to enroll in another clinical trial¹¹;

¹⁰ Includes trials that have a study intervention such as a drug, biologic, or device.

¹¹ Includes trials that could interfere with safety assessment of the investigational product at any time during the study period

18) The PI considers that the subject should not participate in the trial.

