5.2 Withdrawal from the Study, Discontinuation of Study Product, or Study Termination

5.2.1 Withdrawal from the Study or Discontinuation of the Study Product

Subjects may withdraw their consent at any time without penalty or loss of benefits to which they are otherwise entitled.

A Site PI may also withdraw a subject from the study or from receiving the study drug for any reason. Follow-Up safety evaluations will be conducted, if the subject agrees. If a subject withdraws or is withdrawn before completion of this trial, the reason(s) will be recorded in the electronic case report form (eCRF). In either case, the reason for withdrawal will be clearly documented and specifically if the reason for withdrawal was related to study drug intolerance or other adverse event.

The reason(s) for withdrawal from the study might include, but are not limited to, the following:

- Subject no longer meets eligibility criteria;
- subject meets individual halting criteria (listed in [Section 8.7.3](#));
- subject becomes noncompliant;
- medical disease or condition or new clinical finding(s) for which continued participation, in the opinion of the Site PI, might compromise the subject's safety, interfere with the subject's successful completion of this trial, or interfere with the evaluation of responses;
- subject is lost to FU;
- determined by a physician's discretion to require additional therapy not indicated in the protocol to ensure subject's health and well-being. The reason(s) for discontinuation of the study drug might include, but are not limited to;
 - subject becomes pregnant;
 - determined by a physician's discretion to require additional therapy not indicated in the protocol to ensure subject's health and well-being.

The Site PI will be explicit regarding trial FU (e.g., safety FU) that might be carried out if the subject will not receive further study drug. If the subject consents, every attempt will be made to follow all AEs through resolution. The procedures that collect safety data for the purposes of research will be included in the original ICF or the Site PI may seek subsequent informed consent using an IRB/IEC-approved ICF with the revised procedures.

The Site PI will inform the subject that data already collected will be retained and analyzed even if the subject withdraws from this trial.

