
Subjects will be admitted to the CRU on the day before injection (or infusion for Part 3) and the following procedures will be performed:

- On admission to the CRU on Day-1, review inclusion/exclusion criteria to ensure the subject is eligible for enrollment. For Part 3, Day 21, review inclusion criteria numbers 2-7 and 10-11, and exclusion criteria numbers 2-4 and 8-18 (from [Section 5.1.2](#)) to ensure the subject remains eligible for dosing.
- Update medical history.
- Review and update concomitant medications.
- Perform targeted PE.

- Obtain resting vital signs after being at rest for at least 5 minutes.
- Obtain weight, calculate BMI.
- Obtain blood samples for baseline fasting (at least 8 hours) clinical chemistry, hematology, coagulation tests, serum pregnancy test [if female of childbearing potential]); for the Day -1 visit, if clinical chemistry, hematology or coagulation test result(s) are outside of the reference range(s), they may not be repeated; if a result is not considered by the site investigator to be clinically insignificant, the subject is removed from the study.
- For women of child-bearing potential, perform a serum pregnancy test (results must be confirmed negative before dosing).
- Obtain blood and urine samples for safety clinical labs.
- Obtain urine sample for drug screen and urine alcohol.
- Obtain urine sample for cotinine test.
- Part 3 (Cohort 11) only, Day 21 – review Memory Aid.

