6.6 Part 3 (Cohort 11)**6.6.1 Days 1 and 22 – Inpatient CRU**

For Cohort 11, the subject will be randomized to sequence and either the study drug will be administered via SC injection in the morning on Day 1 and as an IV infusion over 60 (± 5) minutes in the morning on Day 22; or the study drug will be administered via IV infusion over 60 (± 5) minutes in the morning on Day 1 and via SC injection in the morning on Day 22. Subjects will be inpatients in the CRU and will undergo the following procedures, which are

listed in the Schedule of Study Procedures and Evaluations ([Appendix A](#)) and detailed in Clinical Evaluations ([Section 7](#)):

- Randomize the subject (Day 1 only).
- Review inclusion criteria numbers 2-7 and 10-11, and exclusion criteria numbers 2-4 and 8-18 (from [Section 5.1.2](#)) to ensure the subject remains eligible for dosing (Day 22 only).
- Obtain resting vital signs before study drug dosing (within 60 minutes of study drug dosing. This is to be documented as the Baseline prior to dosing on Day 1).
- Perform targeted PE.
- Obtain a 12-lead ECG within 60 minutes of study drug dosing, (Day 1 only), after at least 5 minutes in the supine position (triplicate readings, at least 1 minute apart within a 15-minute period).
- Baseline skin assessment at SC injection site area prior to study drug dosing: assess reactogenicity at SC injection site before study drug dosing on Day 22 (see [Section 7.1.3](#) and MOP for this study).
- Administer study drug.
- Obtain vital signs (SC): at 15 minutes (± 5 min), 1 hour (± 10 min), and 2 hours (± 10 min) after dosing, after resting in a supine or semi-supine position for at least 5 minutes.
- Obtain vital signs (IV): at 15 minutes (± 5 min), 1 hour (± 10 min), and 2 hours (± 10 min) after start of infusion, and after resting in a supine or semi-supine position for at least 5 minutes.
- Obtain PK blood samples within 60minutes before study drug dosing and at 0.5 h (± 5 min), 1 h (± 10 min), 2 h (± 10 min), 4 h (± 10 min), 6 h (± 10 min), 8 h (± 10 min), and 12 h (± 10 min) after the start of infusion or injection.
- Post dose ECG (SC) at 4 hours (± 10 minutes) after SC injection, 12-lead ECG after at least 5 minutes in the supine position (triplicate readings, at least 1 minute apart within a 15-minute period).

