7.1.7 Assessment of Concomitant Medications/Treatments Other than Study Product

Subjects are required to abide by the following rules regarding intake of medications and other substances before and during the study:

- 1) Refrain from the use of any prescription medications (with the exception of hormonal contraceptives), within 14 days before the first study drug administration and until after the final study visit.
- 2) Refrain from the use of over-the-counter medications including vitamins, supplements, and herbal supplements (except for acetaminophen or ibuprofen) within 14 days before the first study drug administration,
- 3) The use of tobacco product, including smoking and the use of snuff and chewing tobacco, and other nicotine or nicotine-containing products (including patches), is not permitted by a subject within 90 days of Screening for the study or while a subject is enrolled in the study. A urine test for cotinine will be performed at Screening and upon admission to the CRU.
- 4) Refrain from consuming foods or beverages containing the following substances for the duration of the study:
- 5) Alcohol: ≤ 48 hours before the first study drug administration until discharge. A urine alcohol test will be performed at Screening and upon admission to the CRU.

- 6) Xanthines/caffeine: ≤24 hours before the first study drug administration and until discharge.
- 7) Refrain from receiving a live or killed vaccine, or immunoglobulin, within 14 days prior to dosing.
- 8) The use of illegal drugs is not permitted while a subject is enrolled in this study. A urine drug test will be performed at Screening and upon admission to the CRU.
- 9) Previous participation in this trial, any other rezafungin trial, or any trial involving administration of drug product within 28 days of study drug dosing. Plans to enroll in another clinical trial that could interfere with safety assessment of the investigational product at any time during the study period;

If a subject is unable to comply with the restrictions described above, the subject's continued participation in the study will be re-evaluated by the Investigator, in consultation with the Medical Monitor.

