8.7 Halting Rules

8.7.1 Study Halting Rules

Trial dosing can be halted at any time if medically indicated. Trial dosing will be stopped, and all available safety data will be reviewed by the SMC if any of the following occur:

- Any SAE (regardless of the relationship to the study drug) throughout duration of study.
- 5 or more subjects in study (cumulative among all cohorts) experience a same grade 2 (or higher) related AE (laboratory or systemic) which is coded in the same high-level group term (HLGT) per MedDRA coding, throughout duration of study. Exception to this includes scenarios where there are obvious and acceptable physiological explanations for a Grade 2 or higher abnormality (e.g., Grade 3 hematuria in a menstruating female).
- Any subject experiences skin ulceration of any grade at an injection site.

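### The eligibility re-check before repeat doses does not list exclusion 1 (hypersensitivity), so no express rule bars re-dosing a subject after a non-serious, related allergic reaction

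*Protocol*

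**What the plan says.** Exclusion 1 in Protocol 5.1.2 bars anyone with a "History of any hypersensitivity or allergic reaction to echinocandins or excipients". The excipients it names are mannitol, polysorbate 80 and histidine. The introduction to Section 5 allows no exemptions from the eligibility criteria.

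Eligibility is checked again before each later dose:
- Part 2, Days 8 and 15 (6.5.1), and Part 3, Day 22 (6.6.1): "Review inclusion criteria numbers 2-7 and 10-11, and exclusion criteria numbers 2-4 and 8-18".
- Part 3, readmission (6.3): "For Part 3, Day 21, review inclusion criteria numbers 2-7 and 10-11, and exclusion criteria numbers 2-4 and 8-18".

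The stated purpose in all three places is to confirm that the subject is still eligible for dosing.

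Section 8.7.3 takes an individual subject off further dosing for any SAE, for ulceration at an injection site, or for another condition that the investigator judges to raise the risk unduly. It does not name allergy. Section 8.7.4 stops an infusion for signs of anaphylaxis and forbids restarting it, but says nothing about the other period's dose.

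**The concern.** Exclusion 1 differs from the other omitted exclusions in two ways: checking it needs no test, and the study drug itself can make a subject meet it. A subject who reacts to the Day 1 dose has that history by Day 8 or Day 22.

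The protocol anticipates such reactions. Section 2.3.1 describes possible histamine release reactions with IV rezafungin (most events mild, all transient) and anaphylactic-like reactions with micafungin, another echinocandin. Appendix B grades allergic reaction, and its Grade 3 includes generalized urticaria, which need not meet an SAE criterion.

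A new volunteer with this history is refused by rule. A volunteer who has a non-serious reaction during the trial meets a checklist that skips the criterion describing it. Section 2.3.2 says subjects have no known benefit from taking part, so a clear stop is worth having even where the risk is modest.

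**Working it through.** **Which criteria are left out.** There are 18 exclusions and 11 inclusions.
- Exclusions: {1 to 18} minus {2-4, 8-18} = {1, 5, 6, 7}. The list covers 3 + 11 = 14 of 18.
- Inclusions: {1 to 11} minus {2-7, 10-11} = {1, 8, 9}.

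Exclusions 5, 6 and 7 are viral serology, laboratory values and ECG, which all need tests. Exclusion 1 does not. Its being a history item does not explain the omission, since exclusions 11, 12 and 14-17 are also about past events and are re-checked.

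**What would stop one subject after a related allergic reaction.**
- *Reaction meets an SAE criterion:* 8.7.3 stops further dosing. This is mandatory.
- *Loss of eligibility (5.2.1):* listed as a reason for withdrawal, but under the lead-in "The reason(s) for withdrawal from the study might include, but are not limited to". Permissive.
- *Inclusion 7 (re-checked):* good health means having none of the conditions described in the exclusions, as the investigator sees it. Whether a resolved drug reaction is such a condition is not stated.
- *Inclusion 10 (re-checked):* "Subjects must refrain from over-the-counter and-prescription medications", with a few exceptions. A reaction treated with a disallowed medicine fails this. Under 7.1.7, "continued participation in the study will be re-evaluated by the Investigator, in consultation with the Medical Monitor". An untreated reaction does not reach this route.
- *Exclusion 2 (re-checked):* a clinically significant condition that, in the investigator's opinion, precludes safe participation. Judgement.
- *Exclusion 18 (re-checked):* "The PI considers that the subject should not participate in the trial". Judgement.
- *8.7.3, investigator's judgement; 8.2.3, stop at the discretion of the investigator or Medical Monitor:* both discretionary.
- *8.7.1, count rule:* "5 or more subjects in study (cumulative among all cohorts) experience a same grade 2 (or higher) related AE". One subject cannot trigger it.
- *8.7.2, cohort rule:* needs two or more subjects with the same related Grade 2 event.
- *8.7.2, sentinel rule:* suspends the cohort for a related event of Grade 2 or higher that starts within 72 hours of dosing and has not resolved within 72 hours of onset. Part 3 has no sentinels.
- *8.7.4:* ends the infusion in progress only.

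Only the SAE rule is both mandatory and sure to apply to one subject outside the sentinel pair.

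**Scope.** Inputs are Protocol Tables 2 and 3.
- Part 2: 24 active subjects × 2 later doses = 48.
- Part 3: 10 subjects × 1 Period 2 dose = 10.
- Total: 48 + 10 = 58 repeat active doses in 24 + 10 = 34 subjects.
- Active Part 2 sentinels: 1 × 4 cohorts = 4 subjects, with 4 × 2 = 8 later doses.
- Remainder: 58 − 8 = 50 doses (50/58 = 86%) in 34 − 4 = 30 subjects whose own reaction cannot trigger the sentinel rule. All 50 remain under the SAE rule and the discretionary routes.
- Actual repeat doses (SAP Section 1): 0.

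**Precision lost if one reactor misses later doses.** The protocol plans neither interval below; they only size the loss. Both ratios assume an unchanged SD and do not depend on its value.
- Part 2, 95% CI for a mean, n from 6 to 5: t(0.975, 5)/√6 = 1.049; t(0.975, 4)/√5 = 1.242; ratio 1.18, so about 18% wider.
- Part 3, 90% CI for log F in the 2×2 crossover, 5 + 5 to 5 + 4: t(0.95, 8) × √(0.5 × (1/5 + 1/5)) = 0.832; t(0.95, 7) × √(0.5 × (1/5 + 1/4)) = 0.899; ratio 1.08, so about 8% wider.

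**The case against.** The best defence is that the protocol already covers the case. Loss of eligibility in 5.2.1 is not confined to the re-check subset, and a subject who reacts to rezafungin then meets exclusion 1 as written. Inclusion 7, which is re-checked, brings in the conditions in the exclusions. The schedules in Appendix A (Tables 12 and 13) mark eligibility assessment on the Part 2 dosing days and on Part 3 Day 21 without limiting it to a subset. Section 8.7.1 lets dosing be halted whenever medically indicated. Adverse events are assessed every day in the unit and Part 2 subjects stay there through Day 21, so a reaction is unlikely to be missed. A competent investigator would probably stop the subject.

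Most of this stands, and it is why the point is minor. It does not remove the gap: these routes allow a stop, or support one on a particular reading, but none requires it after a single non-serious reaction. The procedure sections name a specific list, and staff will work from that list.

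A second objection is that leaving mild reactions to judgement is reasonable when later-dose tolerability is a primary objective, because an automatic bar leaves later-dose data from non-reactors only. That cost is real. It weighs less than it seems, because exclusion 1 already bars any such reaction at entry, however mild, and Section 5 allows no exemptions.

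A reader might infer that the protocol permits re-dosing after a serious allergic reaction, or that a first-time reactor can be stopped only by discretion. Neither is supported, since any SAE ends that subject's dosing under 8.7.3 and halts trial dosing for committee review under 8.7.1.

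**Conclusion.** The point holds in a narrow form. All three re-check lists omit exclusion 1, and no express rule bars re-dosing one subject after a non-serious, related allergic reaction. This applies mainly to an untreated reaction in a subject who is not a sentinel. Serious reactions are covered.

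Severity is minor. The 58 and 50 dose counts show how many planned doses the list governs; they should not be read as expected harms or as unprotected doses. The conclusion assumes no reaction rate. It rests on reading the 5.2.1 reasons as permissive and inclusion 7 as unclear about a resolved reaction. If both were read as binding, the change would be a clarification only.

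A reader might also infer that subjects were exposed or that results are affected. The SAP Preface rules this out: no MAD or BA subject was enrolled. The correction matters for the plan as written and for any resumed or successor protocol.

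**What to change.** In Sections 6.3, 6.5.1 and 6.6.1, change the re-check to exclusion criteria numbers 1-4 and 8-18. That covers 15 of the 18 exclusions instead of 14 and is enough on its own; no new bullet in 8.7.3 is needed. Whether a reaction is allergic remains a clinical judgement; the change makes its consequence explicit. An infusion stopped under 8.7.4 for syncope or bradycardia without allergic signs would not, by this change, bar the SC dose.

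The edit is one number in three places, with no new visit, procedure or subject. The downside is that a subject with a mild reaction (Appendix B Grade 1 is itching without rash) may miss later doses. That loses some PK and later-dose tolerability data, on the scale worked out above, and the later-dose tolerability findings would then describe subjects who did not react.

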6.6.2 Days 2 and 23 – Inpatient CRU

- Obtain resting vital signs 24 hours (± 30 min) after being at rest for at least 5 minutes.
- Perform targeted PE.
- Assess reactogenicity at SC injection site at 24 h (± 30 min) post dose (see [Section 7.1.4](#) and MOP for this study).
- Obtain blood for hematology/coagulation/chemistry and urine for urinalysis.
- Obtain PK blood sample 24 hours (± 30 min) after dosing.
- Assess AEs.

